1.5.2. Ketorolac Pharmacology and Pharmacokinetics

Ketorolac tromethamine is a non-steroidal anti-inflammatory drug. The biological activity of Ketorolac tromethamine for pain relief is associated with the S-form. The peak analgesic effect of Ketorolac tromethamine occurs within 2 to 3 hours and is not statistically significantly different over the recommended dosage range of Ketorolac tromethamine. The greatest difference between large and small doses of Ketorolac tromethamine is in the duration of analgesia.

Ketorolac tromethamine is a racemic mixture of [-S]- and [+R]-enantiomeric forms, with the S-form having analgesic activity and the R-form the proposed cancer inhibition effect. The IV dosing of ketorolac is 100% bioavailable. The pharmacokinetic parameters for IV dosing is shown in Table 2. In adults, following IV administration of Ketorolac tromethamine in the recommended dosage ranges, the clearance of the racemate does not change. This implies that the pharmacokinetics of Ketorolac tromethamine in adults, following single or multiple IV doses of Ketorolac tromethamine are linear. At the higher recommended doses, there is a proportional increase in the concentrations of free and bound racemate.

The mean apparent volume ($V\beta$) of Ketorolac tromethamine following complete distribution was approximately 13 liters. This parameter was determined from single-dose data. The Ketorolac tromethamine racemate has been shown to be highly protein bound (99%). Nevertheless, plasma concentrations as high as 10 mcg/mL will only occupy approximately 5% of the albumin binding sites. Thus, the unbound fraction for each enantiomer will be constant over the therapeutic range. A decrease in serum albumin, however, will result in

increased free drug concentrations. The half-life of the Ketorolac tromethamine S-enantiomer was approximately 2.5 hours ($SD \pm 0.4$) compared with 5 hours ($SD \pm 1.7$) for the R-enantiomer. In other studies, the half-life for the racemate has been reported to lie within the range of 5 to 6 hours.

	Tmax (min)	Cmax (mcg/ml) single dose	Cmax (mcg/ml) steady state qid	Cmin (mcg/ml) steady state qid	Cavg (mcg/ml) steady state qid
15 mg	1.1 \pm 0.7	2.47 \pm 0.51	3.09 \pm 0.1.17	0.61 \pm 0.21	1.09 \pm 0.30
30 mg	2.9 \pm 1.8	4.65 \pm 0.7	6.85 \pm 0.7	1.04 \pm 0.7	2.17 \pm 0.7
Tmax = time to peak plasma concentration, Cmax = peak plasma concentration, Cmin = trough plasma concentration, Cavg = average plasma concentration					

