Table 2. Average Pharmacokinetic Parameters for IV Ketorolac

The intraperitoneal distribution of ketorolac and its racemic mixture is unknown and represents the primary endpoint of this trial. Based on the known pharmacokinetics, it is favorable that the half-life of the R-enantiomer is longer and that both are protein bound. We anticipate that the post-op decrease in serum albumin will favor free drug with a high rate of transport into the peritoneal cavity.

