2.0 OBJECTIVES

2.1 Primary Objective

The primary objective of this study is to determine the concentration of measurable levels of R and S- Ketorolac (and the percent racemic mixture) in the peritoneal cavity after IV administration in the post-operative patient after cytoreductive surgery.

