8.0 STUDY MODALITY

8.1 Ketorolac tromethamine (Toradol® Roche Pharmaceuticals)

Formulation: Ketorolac is supplied in sterile single use 1mL vials of 15 mg/mL (**NDC 55390-480-01**) and 30 mg/mL, 1 mL single-dose vials of 30mg/mL (**NDC 55390-481-01**). Supplies are obtained by the University Hospital (University of New Mexico) and stored in the Pyxis until ordered by the treating physician.

Preparation: Ketorolac tromethamine for IV use is supplied in 1 mL vials of either 15mg or 30mg individual dose which requires no reconstitution.

Storage: Vials of ketorolac tromethamine are stored at room temperature protected from light in the carton until use.

Dosing: Ketorolac tromethine will be dosed according to FDA approved recommendations. For planned **single dose (IV)** based on clinical scenario:

- Patients < 65 years of age: One dose of 30 mg.
- Patients ≥ 65 years of age, renally impaired and/or less than 50 kg (110 lbs) of body weight: One dose of 15 mg.

For planned **Multiple-Dose Treatment (IV)** for indicated pain management

- Patients < 65 years of age: The recommended dose is 30 mg ketorolac tromethamine injection every 6 hours. The maximum daily dose for these populations should not exceed 120 mg.

- For patients \geq 65 years of age, renal impaired patients, and patients less than 50 kg (110 lbs): The recommended dose is 15 mg ketorolac tromethamine injection every 6 hours. The maximum daily dose for these populations should not exceed 60 mg.

Adverse Effects: Complications of treatment with ketorolac tromethamine, such as G.I. ulceration, bleeding and perforation, postoperative bleeding, acute renal failure, anaphylactic and anaphylactoid reactions and liver failure have been described. These NSAID-related complications can be serious in certain patients for whom ketorolac tromethamine is indicated, especially when the drug is used inappropriately.

In patients taking ketorolac tromethamine or other NSAIDs in clinical trials, the most frequently reported adverse experiences and frequency are shown in the table below:

	< 1%	1%-10%	>10%
cardiovascular	CHF, palpitation, pallor, tachycardia, syncope	hypertension	
dermatologic	Alopecia, urticaria, photosensitivity	Injection site pain, rashes, pruritis	

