9.0 TREATMENT PLAN

All patients will receive a single dose of IV ketorolac for pain management for the indication of post-operative pain control. The single dose will be considered the study dose for which all consenting eligible patients will receive. The dose of IV ketorolac will be determined per the recommendations in the package insert. Patients less than 65 years of age and in otherwise good health will receive a 30mg IV single dose. Patients 65 years of age or greater, or who have mild renal insufficiency or are of low weight (as per section 3.2) will receive a single 15 mg dose IV ketorolac. In patients who have a clinical pain response and have no contraindications to multi-dose (every 6 hours over 24 hours), additional doses will be given per physician discretion based on clinical indication. Patients receiving 24 hour dosing will be eligible for sample time points after 24 hour dosing.

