Data will be analyzed as a repeated measure ANOVA followed by Tukey's post hoc analysis in order to evaluate whether there are significant differences between groups (pre-and post-ketorolac treatment). We plan to group both dose groups together as we anticipate similar drug measures based on known prior serum pharmacokinetic studies. If we find a large discrepancy in peritoneal ketorolac concentrations between the 15mg and 30mg treated group, we may amend the protocol to increase sample size to evaluate the groups independently. The analysis of demographic characteristics (age and ethnicity) and clinical characteristics, including histologic tumor type, and stage of disease will be descriptive. For the peritoneal distribution study, seven patients should be sufficient for statistically meaningful results based on a study of similar design to measure concentration of doxorubicin in ovarian ascites following IV administration (45).

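### Section 11.2.1 pools 15 mg and 30 mg patients on a premise of similar drug levels that the protocol's own serum data do not support; R and S concentrations should be reported by dose

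*Combined protocol and SAP*

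**What the plan says.** The primary objective (Section 2.1, repeated in 11.2.1) is to determine R- and S-ketorolac concentrations in the peritoneal cavity, together with the percentage of each enantiomer. The target is 7-10 complete sample sets, and the analysis is a repeated-measures ANOVA of pre- against post-dose values with Tukey comparisons.

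On dose, Section 11.2.1 says: "We plan to group both dose groups together as we anticipate similar drug measures based on known prior serum pharmacokinetic studies". It adds that the protocol may be amended to enlarge the sample and study the doses separately if a large gap in peritoneal levels appears. It does not say how large, and the amendment is optional.

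Section 1.5.2 says that over the recommended IV doses "the clearance of the racemate does not change", that the kinetics are linear, and: "At the higher recommended doses, there is a proportional increase in the concentrations of free and bound racemate". Of the peritoneal cavity it says: "The intraperitoneal distribution of ketorolac and its racemic mixture is unknown and represents the primary endpoint of this trial".

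Dose is not assigned at random. Section 8.1 gives the lower dose to patients aged 65 or over and to those who are "renally impaired and/or less than 50 kg (110 lbs) of body weight: One dose of 15 mg". Section 9.0 describes the same group as "Patients 65 years of age or greater, or who have mild renal insufficiency or are of low weight".

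**The concern.** The reason given for pooling is a claim about drug levels, yet the serum data that the protocol presents by dose point to levels that rise with dose. If that holds in peritoneal fluid, a pooled mean of absolute R or S concentration describes neither dose and moves with the mix of patients who happen to yield complete sets. Absolute concentration is the primary endpoint, and nothing in the plan commits to showing it by dose.

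**Working it through.** **The plan's own figure.** Section 11.2.1 starts with 60 recruits and loses 60%: 60 × 0.40 = 24, against the stated 25. It then loses 15-18 more: 25 − 18 = 7 and 25 − 15 = 10. The target of 7-10 is reproduced, and it covers both doses together. No SD, effect size or power is given, so the statement that seven patients suffice cannot be recomputed.

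**Serum ratios.** These use the Table 2 means (racemate, mcg/ml). I do not use the 30 mg SDs: all four concentration columns show 0.7, which is doubtful.

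| Measure | 15 mg | 30 mg | Ratio 30:15 |
|---|---|---|---|
| Cmax, single dose | 2.47 | 4.65 | 1.88 |
| Cmax, steady state | 3.09 | 6.85 | 2.22 |
| Cmin, steady state | 0.61 | 1.04 | 1.70 |
| Cavg, steady state | 1.09 | 2.17 | 1.99 |

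All four are compatible with rough proportionality. None shows similar concentrations at the two doses.

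**Effect of dose mix on a pooled mean.** Let r be the 30:15 ratio and k the number of 7 patients on 15 mg. In units of the 15 mg mean, the pooled mean is (k + (7 − k)r)/7. The mixes k = 2 and k = 5 are illustrative.

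- r = 2 (the stated proportionality): (2 + 10)/7 = 1.714 and (5 + 4)/7 = 1.286, a fall of 25%.
- r = 1.70: (2 + 8.50)/7 = 1.500 and (5 + 3.40)/7 = 1.200, a fall of 20%.
- r = 2.22: (2 + 11.10)/7 = 1.871 and (5 + 4.44)/7 = 1.349, a fall of 28%.
- r = 1 (lower dose fully offset by slower clearance): no change.

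In Table 2 units, pooled Cavg would be (2 × 1.09 + 5 × 2.17)/7 = 1.86 with two patients on 15 mg and (5 × 1.09 + 2 × 2.17)/7 = 1.40 with five.

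**Which analyses are exposed.** Section 4.2 excludes ketorolac or other NSAID use before the study dose, so pre-dose concentration should be about zero. The pre/post difference in concentration is then essentially the absolute post-dose level, and the ANOVA on concentration is exposed in the same way as the mean. The R:S percentage is formed within a sample, so under linear kinetics dose largely cancels. The trend analysis in Section 11.2.2 uses each patient's measured R concentration. Both are less affected.

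**Would a two-fold gap be noticed?** If the amendment trigger were run as a two-sided 5% t test on log concentrations, power for a two-fold difference with 3 against 4 patients would be 70%, 27% or 15% at assumed CVs of 30%, 60% or 100%. With 5 against 5 it would be 90%, 41% or 21%. The documents give no CV for peritoneal levels.

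**The case against.** The best defence is that Section 1.5.2 describes what dose does in adults generally, whereas Section 11.2.1 speaks of two different kinds of patient. Older, lighter or mildly renally impaired patients may clear ketorolac more slowly, so 15 mg in them could approach 30 mg in the others. This is possible, and it means the two sections do not strictly contradict each other. But equal average exposure would need about half the clearance (15/30 = 0.5), and Section 4.2 excludes creatinine clearance below 60 ml/min, which limits what renal function could contribute. The protocol makes no such argument and gives no kinetics for these patients. Its remark that peak analgesia differs little across doses concerns an effect, not a concentration.

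It is also fair that the Table 2 ratios fit the trial poorly. They are racemate values; three are at steady state, and the fourth is a peak reached within minutes. None is an R or S level at 1, 6 or 24 hours. They show that the premise lacks support, not what the peritoneal ratio will be.

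The plan does not say that a pooled mean will be the only presentation, and its amendment clause implies that someone will look at levels by dose. That stands, but looking is not a commitment to report.

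Lastly, sampling error is not small. The three legible 15 mg CVs in Table 2 (0.51/2.47 = 21%, 0.30/1.09 = 28%, 0.21/0.61 = 34%) give a standard error for a mean of 7 of about 8% to 13%. A 25% shift exceeds that; a shift from a smaller dose gap might not.

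**Conclusion.** The point holds in a limited form. The premise for pooling is unsupported by anything in the documents, and the only dose-specific serum data lean against it. A pooled absolute R or S concentration, and the pre/post ANOVA on concentration, may depend on the dose mix. The 25% figure rests on exact proportionality, on peritoneal levels following plasma, and on an illustrative change from 2 to 5 of 7 patients on 15 mg. The real effect could be anywhere from negligible upward.

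A reader might infer that 30 mg patients will have about twice the peritoneal level of 15 mg patients. The documents do not support that: dose is tied to age, weight and renal function, and peritoneal distribution is stated to be unknown. A reader might also infer that pooling undermines every endpoint. It does not; the R:S percentage and the concentration-based trend analysis are less affected. This is a reporting weakness in the primary endpoint, worth correcting but no threat to the trial as a whole.

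**What to change.** In Section 11.2.1:

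- Delete the premise of similar drug levels, or support it with kinetic data for these two patient groups.
- As the primary presentation, report absolute R and S concentrations in peritoneal fluid and serum at each time-point by dose received (15 mg or 30 mg), with individual values and descriptive summaries.
- Allow the R:S percentage to be pooled.
- Define how large a gap between doses would trigger the amendment, or drop the clause.

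The cost is some rewording and one table or listing, with no extra patients, samples or assays. The drawback is that each dose group will be very small and confounded with age, weight and renal function, so the by-dose results are descriptive and cannot test a dose effect. The change concerns analysis and reporting only, not which dose a patient receives.

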11.2.2 Secondary Endpoints

We will determine the effect of IV ketorolac on cell adhesion and migration on ovarian cancer cells retrieved from the peritoneal cavity after cytoreductive surgery using several different biologic assays. Isolated cells will be tested for evidence of target inhibition and functional changes in adhesion and migration. Target activity assays: Rac1 and Cdc42 activity will be measured in cells using effector binding assays (GLISA) that are

commercially available (Cytoskeleton, Inc) and are used to determine activity of primary cells ex vivo as we have demonstrated in (Fig. 1C). In addition, we will conduct qRT-PCR analysis of cells isolated pre and post ketorolac administration to test for expression of genes downstream of Rac1 and Cdc42 activation that were validated in cell culture and in vivo studies. Adhesive properties of cells will be measured by assays for spreading and adhesion. For spreading analysis, cells will be rinsed in Dulbecco's PBS (DPBS) and plated on coverslips without or with extracellular matrix coating and images will be obtained at regular intervals. Spreading is defined as flattened cells without the refractile, fibroblastic morphology determined and expressed as a percentage of the total cells \pm SD as we've described previously (46). For adhesion, cells will be plated onto 96 well plates without or with extracellular matrix coating and incubated for 30 min. Cells will be fixed and non-adherent cells will be removed by gentle washing. Colorimetric quantification of adherent cells will be performed using standard protocols. Migration will be measured after plating cells on collagen-coated coverslips in assessing migration by time lapse photography on a heated microscope stage (UNM Microscopy Facility). Distance traversed for individual cells will be quantified by image analysis software. Data will be analyzed as a repeated measure ANOVA followed by Tukey's post hoc analysis in order to evaluate whether there are significant differences between groups (pre-and post-ketorolac treatment). Trend analyses of response will also be performed based on peritoneal R-ketorolac concentrations.

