10.1 Pre-treatment Sample Collection

- Collection of ascites cells at the time of tumor debulking
- Collection of peritoneal fluid and cells by the PI ([name]) or the co-PI's ([name] and [name]) and blood prior to ketorolac administration.

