10.3.4. Spreading, Adhesion, and Migration Assays of Patient Derived Peritoneal Cells

The impact of ketorolac treatment on residual ovarian tumor cell behavior will be assessed by measuring time for cell adhesion and spreading, as well as migration distance as follows. All of the assays require only small numbers of cells. CYTOO chips (see 5.6.5 and Fig. 7) will serve as an alternate measure for assessing cell adhesion and spreading. Controls: patient cell adhesion prior to treatment; cell adhesion when incubated with 100 μ M R-ketorolac.

10.3.4.1. Spreading: Cells (100-5,000/sample) will be rinsed in Dulbecco's PBS (DPBS) and plated on coverslips without or with extracellular matrix coating and images will be obtained at regular intervals. Spreading is defined as flattened cells without the refractile, fibroblastic morphology determined and expressed as a percentage of the total cells \pm SD.

10.3.4.2. Adhesion: Cells (100-5,000/well) will be plated onto 96 well plates without or with extracellular matrix coating and incubated for 30 min. Cells will be fixed and non-adherent cells will be removed by gentle washing. Colorimetric quantification of adherent cells will be performed using standard protocols.

10.3.4.3 Migration: Cells (100-5,000/sample) will be placed on collagen-coated coverslips in culture medium and migration will be measured by time lapse photography on a heated microscope stage (UNM Microscopy Facility). Distance traversed for individual cells will be quantified by image analysis software.

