10.3.5. PCR analysis of Patient Derived Peritoneal Cells

Genes downstream of Rac1 and Cdc42 activation, which have been validated in cell culture and through in vivo studies (e.g. PAK, IQGAP, DOCK-180, CRK, WAVE3) will be tested by quantitative real time PCR using human genome predesigned and validated primer sets and assay kits from Origene (Rockville, MD). Each assay will be performed in duplicate and ketorolac response will be established by comparison of pretreatment versus treatment samples. A >2-fold change between 0 treatment and subsequent treatment time-points

would be considered significant. This assay will be performed only when sufficient cell numbers are present in the peritoneal fluid (>10,000 cells) to allow purification of RNA.

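### Sections 11.2.2 and 10.3.5 read pre/post change in patient cells as a ketorolac effect, but those assays cannot separate drug from time since surgery, and the planned concentration trend analysis is unspecified

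*Combined protocol and SAP*

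**What the plan says.** The combined protocol and SAP describes a single-arm pilot. Section 9.0: "All patients will receive a single dose of IV ketorolac".

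Section 11.2.2 sets the secondary aim: "We will determine the effect of IV ketorolac on cell adhesion and migration". The specified test is: "Data will be analyzed as a repeated measure ANOVA followed by Tukey's post hoc analysis", with pre- and post-ketorolac samples as the groups compared. Section 10.3.5 is more direct for the PCR assay: "ketorolac response will be established by comparison of pretreatment versus treatment samples", with a change of more than two-fold taken as significant.

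The controls for the spreading, adhesion and migration assays are in Section 10.3.4: "Controls: patient cell adhesion prior to treatment; cell adhesion when incubated with 100" μM R-ketorolac. They are the patient's own earlier cells and cells spiked with drug.

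Section 11.2.2 then adds: "Trend analyses of response will also be performed based on peritoneal R-ketorolac concentrations". It gives no model, no adjustment for time and no statement of how this result bears on the conclusion.

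Section 10.1 lists two drug-free cell collections: "Collection of ascites cells at the time of tumor debulking", and a later one before ketorolac is given. The table in Section 10.3 labels timepoint 1 as predose. Post-dose samples follow at 1, 6 and 24 h, with 48 h only for patients on elective multiple dosing. Section 11.2.2 does not say which drug-free sample is the baseline.

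**The concern.** The patients have just had cytoreductive surgery. Cell mix and inflammation in the peritoneal cavity may change over the next 24 h whether or not ketorolac is given. With no undosed patients followed over the same hours, a pre/post difference contains drug effect and recovery together, and the specified test cannot divide them. A significant result would be reported as an effect of ketorolac, although the comparison does not identify one.

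Two details add to this. The 24 h sample counts as post-ketorolac even in single-dose patients, who by the plan's serum half-lives have almost no drug left by then. And if the debulking cells served as baseline, the change caused by the operation itself would fall inside the contrast.

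The documents show that the target can move without drug: Section 1.2 reports that Rac1 and Cdc42 activity in fresh tumor isolates fell after 48 h in culture. That is ex vivo, so it shows only that drift is plausible, not how large it is in patients.

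**Working it through.** **1. Number of sets (Section 11.2.1).** 60 recruits × (1 − 0.60) = 24, against the stated 25 with a port. 25 − 15 = 10 and 25 − 18 = 7, which reproduces the target of 7-10 complete sets. The plan gives no alpha, effect size, SD or power for the secondary endpoint. Assumed here: two-sided 0.05 and residual SD 1.

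**2. Overall ANOVA with drift and no drug effect.** Model: response = patient + d × (t/24) + error, at t = 0, 1, 6, 24 h, with d in residual SDs.
- The drift shape is 0, 0.042, 0.25, 1, with mean 0.323. The sum of squared deviations is 0.104 + 0.079 + 0.005 + 0.458 = 0.647 (from unrounded terms).
- The noncentrality is λ = n × d² × 0.647, with 3 and 3(n − 1) degrees of freedom.
- n = 7 (critical F 3.16): d = 0.5, 1, 2 give λ = 1.13, 4.53, 18.1 and rejection in 11%, 33%, 91%.
- n = 10 (critical F 2.96): λ = 1.62, 6.47, 25.9 and rejection in 15%, 49%, 99%.

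**3. Tukey, any post-dose time versus predose.** The difference needed is q × s/√n: 4.00/√7 = 1.51 SD at n = 7 and 3.87/√10 = 1.22 SD at n = 10. Simulated rates with no drug effect and linear drift:

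| Drift over 24 h (residual SD) | n = 7 | n = 10 |
|---|---|---|
| 0 | about 3% | about 3% |
| 0.5 | about 6% | 8-9% |
| 1 | about 22% | about 34% |
| 2 | about 81% | about 95% |

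Almost all of these come from the 24 h contrast. In a 20,000-replicate check at n = 7 and d = 1, that contrast alone was significant in 20% of trials, against 21% for any contrast. If drift is half complete at 1 h and complete by 6 h, the 1 SD rates are 31-33% (n = 7) and 47-48% (n = 10).

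**4. Drug left in single-dose patients.** Section 1.5.2: "The half-life of the Ketorolac tromethamine S-enantiomer was approximately 2.5 hours", and 5 h for R.
- R: 2^(−1/5) = 87%, 2^(−6/5) = 44%, 2^(−24/5) = 3.6% at 1, 6 and 24 h.
- S at 24 h: 2^(−24/2.5) = 0.13%.

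These are serum figures. Section 1.5.2 says that the intraperitoneal distribution is unknown.

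**5. Concentration models.** Simulation with 3,000 runs per setting. Assumptions: peritoneal R-ketorolac falls with the serum half-life (5 h, SD 1.7), 40% of patients on 15 mg, log-SD 0.4 between patients, and none or half of the patients on repeat doses.

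- *Planned trend, with patient effects but no time term.* With single dosing and linear drift, false positives are 10-12% at 1 SD and 18-26% at 2 SD (9-27% in a repeat run). In most other settings they are near 5% or below; the exceptions reach 16%, for early 2 SD drift with repeat dosing.
- *Patient + categorical time + concentration.* False positives are 4-6% in every setting. Power for an effect of 1 SD at the typical initial 30 mg concentration is 12-17% (n = 7) and 16-26% (n = 10); for 2 SD it is 32-48% and 46-66%. For an effect of 1 SD per mcg/mL, a separate run gave 10-20%. Power is low because removing time leaves only 18-20% of the within-patient variance in concentration (single dose), or 34-36% (half on repeat doses).
- *Patient + linear time + concentration.* Power at 1 SD is 33-54%. False positives are about 5% if drift is linear, but 17-43% for a 2 SD drift complete by 6 h as in step 3. Other fast shapes gave 12-20% (exponential, 3 h time constant, single dosing) and 5-8% (straight ramp to 6 h). If the response follows concentration one sample late, the concentration term found a true effect of 2 SD per mcg/mL in 2% of trials at n = 7, against 49% for Tukey.

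**The case against.** The strongest reply is that the plan does not rest on pre/post comparison alone. Section 11.2.2 also plans the R-ketorolac trend analysis, which is much less exposed to drift than the ANOVA. Section 10.3.4 includes cells incubated with R-ketorolac. Sections 10.3.2 and 10.3.3 test peritoneal fluid on cultured cells against predose fluid and R- and S-ketorolac controls, which removes changes in the patient's cell mix, though not changes in the fluid. Section 10.3 labels timepoint 1 as predose, so the baseline is a wording gap more than an open choice. This is also a feasibility pilot, and the endpoint is secondary.

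Most of that stands. A reader might infer that a pre/post difference is the only evidence the plan would use; the trend sentence rules that out. But the trend has no time adjustment and no role in attribution, while Section 10.3.5 states outright that pre/post comparison establishes the response. Pilot status excuses a small sample, not the label put on the result.

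A reader might also infer that the planned samples let drug and recovery be separated cleanly, so that a linear-time model could be the sole basis for claiming an effect. The documents do not support this. Peritoneal concentrations are unknown until the primary endpoint is measured. Patients on repeat doses need not wash out by 24 h. The linear model is protected only for some drift shapes, and it misses a delayed response, which is possible for gene expression. The 15 mg dose follows age, renal function and weight, and repeat dosing follows pain response and clinical indication, so concentration is partly confounded.

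**Conclusion.** The point holds in a limited form. In a single-arm study, Sections 11.2.2 and 10.3.5 attribute pre/post change in patient-derived cells to ketorolac, and nothing in those assays separates drug from time since surgery. The ANOVA/Tukey test is sound if there is no drift. Its false-positive rate as a test of drug effect reaches about one in five (n = 7) to one in three (n = 10) at a linear drift of 1 residual SD, and most trials at 2 SD. At 0.5 SD the Tukey inflation is small.

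The percentages rest on assumed drift size and shape, and those for the concentration models also on an assumed peritoneal profile. That drift biases attribution does not rest on those assumptions. The documents do not show that drift of this size occurs, so it would be wrong to say that the trial will report a false drug effect. What they show is that it could not tell one from a real effect by the stated comparison. A better-specified trend analysis can support attribution from samples already planned, but with 7-10 sets it cannot settle it.

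**What to change.** 1. In 11.2.2 and 10.3.5, report the pre/post ANOVA, Tukey and fold-change results as *change after surgery and ketorolac*, not as a ketorolac effect or response.
2. Specify the planned trend analysis for each assay: patient effects so that the comparison is within patient, sampling time as a category, and R-ketorolac measured in the same peritoneal sample. Show linear time as a sensitivity analysis with more power that depends on the shape of the drift. Label the result exploratory and supportive, to be read alongside the in vitro fluid assays and the R and S controls.
3. Name the post-operative predose sample (timepoint 1) as baseline. Report the debulking-to-predose change and, in single-dose patients, the 24 h sample as descriptive checks on drift.
4. State the limits: low power, so a null result does not show absence of effect; insensitivity to delayed responses; confounding of concentration with patient characteristics and clinical indication; and a peritoneal profile not known in advance.

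The cost is SAP wording and a little more analysis. No new samples, patients or control arm are needed. The trial gives up a direct claim of a ketorolac effect from the pre/post test, which the design could not support.
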